8.3.5 Pregnancy

If a pregnancy is reported, the investigator should inform the sponsor within 24 hours of learning of the pregnancy and should follow the procedures outlined in Appendix 4, Section 10.4.

If a participant inadvertently becomes pregnant while on study intervention, the participant will be immediately discontinued from study treatment. The site will contact the participant at least monthly and document the participant's status until the pregnancy has been completed or terminated. The outcome of the pregnancy will be reported to the sponsor without delay and within 24 hours if the outcome is a serious adverse experience (e.g., death, abortion, congenital anomaly, or other disabling or life-threatening complication to the mother or newborn). The study investigator will make every effort to obtain permission to follow the outcome of the pregnancy and report the condition of the fetus or newborn to the sponsor.

It is unknown whether pembrolizumab or regorafenib is excreted in human milk. Since many drugs are excreted in human milk, and because of the potential for serious adverse reactions in the nursing infant, participants who are breastfeeding are not eligible for enrollment.

All pregnancies and exposure during breastfeeding must be reported by the investigator, from the start of study intervention through 120 days following withdrawal of study intervention, or 30 days following withdrawal of study intervention if the participant initiates new anti-cancer therapy. Details of all pregnancies in female participants and, if indicated, female partners of male participants will be collected after the start of study intervention and until outcome.

Abnormal pregnancy outcomes (e.g., spontaneous abortion, fetal death, stillbirth, congenital anomalies, ectopic pregnancy) are considered SAEs.

For a pregnancy in the partner of a male study participant, all efforts will be made to obtain similar information on course and outcome, subject to the partner's consent.

For all reports, the forms provided are to be used. The investigator should submit them within the same timelines as an SAE.

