g. If pembrolizumab is permanently discontinued first and the day 90 safety follow-up visit after the last dose of pembrolizumab falls into the regorafenib treatment period or regorafenib day 30 safety follow-up period, no separate pembrolizumab day 90 safety follow-up visit is necessary as the information gathering and examinations will occur with regorafenib treatment cycle visit, EoT visit, or day 30 safety follow-up visit (required for either regorafenib, pembrolizumab, or combination). All pregnancies and exposure during breastfeeding should be collected from the start of study intervention through 120 days following discontinuation of study intervention, or 30 days following discontinuation of study intervention if the participant initiates new anti-cancer therapy

h. Every 6 weeks (±7 days) until PD during the first 54 weeks of treatment; every 9 weeks (±7days) until PD afterwards

i. Study intervention-related AEs only

j. Optional; however, Panel A is required on W1D1 if screening tests were not completed within 7 days of first study intervention.

08 JUN 2021 Page 24 of 141

1.3.2 **Biomarker Sampling**

Table 1-2: Schedule of Biomarker Blood Sampling

	Scree	ening				Inte	rvent	tion F	Perio	d (we	eks)ª				End of treatment (DC)
Procedure	Within 28 days prior to the first dose	Within 7 days prior to the first dose	W1 D1	W2 D1	W3 D1	W4 D1	W5 D1	W6 D1	W7 D1	W8 D1	W9 D1	W13 D1	W19 D1	W25 D1	Within 14 days after last dose or DC decision (DC of both rego and pembro)
								± 3	days	,					+ 7 days
Whole blood for pharmacogenetics			Х												
Biomarker blood for flow cytometry 1 ^b		Х	Х	х			Х		Х		Х	Х	Х	Х	Х
Biomarker blood for flow cytometry 2 ^b		Х	Х	Х			Х		Х		Х	х	Х	Х	Х
Biomarker serum		Х	Х	Х			Х		Х		Χ	Х	Х	Х	Х
Biomarker plasma		Х	Х	Х			Х		Х		Х	Х	Х	Х	Х
Biomarker plasma for ctDNA		Х	X				Х		Х			х	Х	х	Х

ctDNA = circulating tumor deoxyribonucleic acid; D = day; DC = discontinuation of study intervention; pembro = pembrolizumab; W = week(s)
a: All samples are to be collected pre-dose.
b. Blood will be collected for flow cytometry from participants enrolled in the expansion phase only, and may only be collected in a subset of participants.

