4.1.1.3 Active Follow-up

A mandatory safety follow-up visit will take place 30 days (window of +7 days) after the last administration of the last study intervention (regorafenib and/or pembrolizumab).

If applicable, an additional safety follow-up must occur 90 days (window of +7 days) after the last pembrolizumab administration. Longer safety follow-up for pembrolizumab is required due to the long half-life of the antibody. Note: If pembrolizumab is permanently discontinued first and the day 30 or the day 90 safety follow-up visit after the last infusion of

Page 38 of 141

pembrolizumab falls into the regorafenib treatment period or regorafenib day 30 safety follow-up visit, no separate pembrolizumab day 30 or day 90 safety follow-up visit is necessary as the information gathering and examinations will occur with regorafenib treatment cycle visit, EoT visit, or day 30 safety follow-up visit. If regorafenib is discontinued first and the day 30 safety follow-up visit falls into pembrolizumab treatment or pembrolizumab day 30 follow-up visit, no separate regorafenib safety follow-up visit is necessary.

All pregnancies and exposure during breastfeeding should be collected from the start of study intervention through 120 days following discontinuation of study intervention, or 30 days following discontinuation of study intervention if the participant initiates new anti-cancer therapy.

Participants who discontinue study intervention due to radiologically confirmed PD will complete the mandatory safety follow-up visits.

Participants who discontinue from the study for any reason other than PD (or death, withdrawal of consent, or lost to follow-up) will be followed for progression during the active follow-up period. During the active follow-up period, computed tomography (CT) / magnetic resonance imaging (MRI) evaluations will be performed at efficacy follow-up visits (see the SoA in Section 1.3.1). In addition, study intervention-related toxicity/AE, information about survival status, and subsequent anti-cancer therapy will be followed up until completion of the active follow-up.

Active follow-up will be terminated by radiological PD, or the start of a new anti-cancer treatment, or death, or withdrawal of consent for further participation, or lost to follow-up.

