 - A male participant must agree to use highly effective contraception (see Appendix 4, Section 10.4.2) during the intervention period and for 120 days after the last dose of regorafenib and refrain from donating sperm during this period.
 - A female participant is eligible to participate if she is not pregnant (see Appendix 4, Section 10.4.3), not breastfeeding, and at least one of the following conditions applies:
 - a) Not a woman of childbearing potential (WOCBP) as defined in Appendix 4, Section 10.4.1.

Page 45 of 141

b) A WOCBP who agrees to follow the contraceptive guidance in Appendix 4, Section 10.4.2 during the study intervention period and for at least 120 days after the last dose of pembrolizumab, and 210 days after the last dose of regorafenib.

Informed Consent

15. Capable of giving signed informed consent as described in Appendix 1 (Section 10.1), which includes compliance with the requirements and restrictions listed in the ICF and in this protocol.

Participants must provide a signed informed consent before any screening procedures.

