10.4.2 Contraception

Regorafenib and pembrolizumab may have adverse effects on a fetus *in utero*. Furthermore, it is not known if pembrolizumab has transient adverse effects on the composition of sperm.

Participants should be informed that taking the study medication may involve unknown risks to the fetus (unborn baby) if pregnancy were to occur during the study. In order to participate in the study, male participants must agree to use highly effective contraception during the treatment period and for 120 days after the last dose of regorafenib. Female participants of childbearing potential must adhere to the contraception requirement (from the day of study intervention initiation, or 14 days prior to the initiation of study intervention for oral contraception) throughout the study period and for 120 days after the last dose of pembrolizumab, and 210 days after the last dose of regorafenib, whichever occurs last. If there is any question that a participant of childbearing potential will not reliably comply with the requirements for contraception, that participant should not be enrolled in the study.

Page 111 of 141

Contraception guidance:

The investigator or a designated associate is requested to advise the participants how to achieve highly effective birth control.

Male participants

Male participants with female partners of childbearing potential are eligible to participate if they agree to the following (as applicable) during the protocol-defined time frame in Section 5.1:

- Are abstinent from sexual intercourse as their usual and preferred lifestyle (abstinent on a long-term and persistent basis) and agree to remain abstinent.
- Agree to use a male condom plus partner use of a contraceptive method with a failure rate of <1% per year as described in Table 10–4 when having sexual intercourse with a WOCBP who is not currently pregnant.
- Men with a pregnant or breastfeeding partner must agree to remain abstinent or use barrier contraception during each episode of sexual intercourse during the protocoldefined time in Section 5.1.
- Refrain from donating sperm during the protocol-defined time frame in Section 5.1.

Female participants

Female participants of childbearing potential are eligible to participate if they agree to use a highly effective method of contraception consistently and correctly as described in Table 10–4 and during the protocol-defined time frame in Section 5.1:

Table 10-4: Highly Effective Contraceptive Methods

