10.4.3.2 Collection of Pregnancy Information

Female participants who become pregnant

- The investigator will collect pregnancy information on any female participant who becomes pregnant while participating in this study. Information will be recorded on the appropriate form and submitted to the sponsor within 24 hours of learning of a participant's pregnancy.
- The participant will be followed to determine the outcome of the pregnancy. The investigator will collect follow-up information on the participant and the neonate, after obtaining the signed informed consent from both parents of the neonate, unless local law or specific circumstances of the respective case allow otherwise, and the information will be forwarded to the sponsor. Generally, follow-up will not be required for longer than 6 to 8 weeks beyond the estimated delivery date. Any termination of pregnancy will be reported, regardless of fetal status (presence or absence of anomalies) or indication for the procedure.
- While pregnancy itself is not considered to be an AE or SAE, any pregnancy complication or elective termination of a pregnancy will be reported as an AE or SAE.
- A spontaneous abortion is always considered to be an SAE and will be reported as such.
- Any post-study pregnancy related SAE considered reasonably related to the study treatment by the investigator will be reported to the sponsor as described in Section 8.3.4. While the investigator is not obligated to actively seek this information in former study participants, he or she may learn of an SAE through spontaneous reporting.
- Any female participant who becomes pregnant while participating in the study will be immediately discontinued from study treatment.

Page 113 of 141

Male participants with partners who become pregnant

- The investigator will attempt to collect pregnancy information on any male participant's female partner who becomes pregnant while the male participant is in this study. This applies only to male participants who receive study intervention.

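### For women, the dated pregnancy-reporting window ends up to 90 days before the contraception period that the protocol requires of them

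*Protocol*

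**What the plan says.** **Dated reporting window.** Protocol section 8.3.5 requires pregnancies and breastfeeding exposure to be reported "from the start of study intervention through 120 days following withdrawal of study intervention". The same sentence then offers a shorter alternative for those who move on to another treatment: "or 30 days following withdrawal of study intervention if the participant initiates new anti-cancer therapy". Section 4.1.1.3 repeats the standard window: "All pregnancies and exposure during breastfeeding should be collected from the start of study intervention through 120 days". So does footnote g to the Schedule of Activities: "All pregnancies and exposure during breastfeeding should be collected from the start of study intervention through 120 days following discontinuation of study intervention". Both also carry the 30-day alternative.

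**Contraception period.** For women of childbearing potential, inclusion criterion 14b runs to "120 days after the last dose of pembrolizumab, and 210 days after the last dose of regorafenib". Section 10.4.2 settles which date governs: "210 days after the last dose of regorafenib, whichever occurs last". For men, criterion 14 requires contraception "for 120 days after the last dose of regorafenib and refrain from donating sperm during this period".

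**Undated duties.** Section 8.3.5 opens with a duty to tell the sponsor of a reported pregnancy inside 24 hours and to follow Appendix 4. It goes on to collect details until the outcome is known. In Appendix 4, section 10.4.3.2 says: "The investigator will collect pregnancy information on any female participant who becomes pregnant while participating in this study". It also sets a 24-hour limit for submission. Neither duty names a last day.

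**The concern.** The protocol treats women as needing contraception for up to 210 days after regorafenib, yet the only reporting window with an end date can close at day 120. Contraception can fail on days 121 to 210. A site that takes the dated window as its rule would then have no dated instruction to report the pregnancy, although the protocol still regarded the woman as needing protection.

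The order of stopping that gives the full gap is a planned one. Section 4.1.1.2 ends pembrolizumab at 18 infusions and lets regorafenib go on beyond two years. It also lets either drug continue alone when the other is stopped for toxicity.

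Routine contacts are unlikely to close the gap. Section 4.1.1.4 lists survival and subsequent anti-cancer treatment as the content of long-term follow-up, not pregnancy. Scheduled pregnancy testing in the Schedule of Activities ends at the later of the safety visit and four months after pembrolizumab.

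At stake is the completeness of pregnancy reports. The response-rate analysis is not affected.

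**Working it through.** **Inputs**

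- Standard reporting window: 120 days after withdrawal of study intervention (8.3.5, 4.1.1.3, footnote g).
- Reporting window after new anti-cancer therapy: 30 days (same places).
- Women's contraception: the later of pembrolizumab + 120 and regorafenib + 210 days (criterion 14b, 10.4.2).
- Men's contraception: regorafenib + 120 days (criterion 14, 10.4.2).
- Assumption: withdrawal of study intervention means the last dose of whichever drug stops last.

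**Formulas.** Count days from the last regorafenib dose. Let L be the number of days by which the last pembrolizumab dose follows it, with L = 0 if regorafenib stops last or both stop together.

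- Women's contraception ends at max(210, L + 120).
- Standard reporting ends at L + 120, so the gap is max(210, L + 120) − (L + 120) = max(0, 90 − L).
- With the 30-day cut-off, reporting ends at L + 30, so the gap is max(210, L + 120) − (L + 30) = max(90, 180 − L).

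| L (days) | Contraception ends | Standard window ends | Gap | 30-day window ends | Gap |
|---|---|---|---|---|---|
| 0 | 210 | 120 | 90 | 30 | 180 |
| 30 | 210 | 150 | 60 | 60 | 150 |
| 60 | 210 | 180 | 30 | 90 | 120 |
| 90 | 210 | 210 | 0 | 120 | 90 |
| 120 | 240 | 240 | 0 | 150 | 90 |

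Beyond L = 90 the gaps stay at 0 and 90 days. The standard-window gap therefore runs from 0 to 90 days, and the 30-day gap from 90 to 180.

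**Men, standard window.** Contraception ends at day 120 and reporting at L + 120, which is never earlier. The gap is 0.

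**Chance contact in the gap.** Taking three months as about 91 days, with ±14 days on each call, consecutive long-term calls lie 63 to 119 days apart. About one call falls in a 90-day gap.

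**Residual drug at day 120.** Section 2.2.2.1 gives metabolite M-5 a mean half-life of about 60 hours, with a range up to 100. Since 120 days is 2,880 hours, that is 2,880 / 60 = 48 half-lives, or 2,880 / 100 = 28.8 at the slow end.

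**The case against.** The strongest reply is that the passages can all be obeyed at once. None of the three dated places tells a site to ignore a later pregnancy. Section 8.3.5 itself begins with an undated 24-hour duty, points to Appendix 4 and follows details to outcome. Section 10.4.3.2 covers any pregnancy during participation. Under section 7, stopping treatment is not in itself leaving the study, and under 4.1.1.4 survivors move into long-term follow-up. A site that follows the wider duty breaks nothing. This stands. A reader might infer that the protocol contradicts itself, or that a pregnancy on days 121 to 210 carries no reporting duty at all; the documents support neither. What remains is that nothing says which scope prevails, and the narrower one is stated three times.

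Second, no document requires the reporting and contraception periods to be equal, and the half-life figures give no exposure reason to extend reporting. This also stands, and a reader should not infer material fetal exposure in the gap. The amendment log ties the contraception duration to the Investigator's Brochure, which was not available for this review. The log names sections 5.1 and 10.4.2 for that change. The reporting sections may simply not have been revisited, but that is inference.

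Third, other rules catch the serious cases. Abnormal pregnancy outcomes count as SAEs (8.3.5), and a related pregnancy SAE that comes to light after the study is still reported (10.4.3.2). An uneventful pregnancy is not an SAE, so these rules cover only part of the gap.

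Finally, a reader might extend the point to men, because exclusion criterion 1 mentions fathering children through 210 days after regorafenib. That is a screening criterion. Men's contraception duty is 120 days, and the standard window covers it.

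**Conclusion.** The point holds as an inconsistency of scope. For women of childbearing potential, the explicit 120-day reporting window is up to 90 days shorter than the required contraception period. The full 90 days applies when regorafenib stops last or together with pembrolizumab. The gap is nil when pembrolizumab outlasts regorafenib by 90 days or more. After new anti-cancer therapy it is 90 to 180 days.

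The figures rest on reading withdrawal of study intervention as the last dose of the last drug. The statement that the undated duties plausibly cover days 121 to 210 rests on reading study participation to include long-term follow-up.

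The impact is minor. It concerns safety reporting only, and few participants are likely to be affected. The documents do not give the number of women of childbearing potential, and the SAP version history records that recruitment stopped early. Efficacy conclusions do not change. This is worth correcting when the protocol is next amended.

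**What to change.** In section 8.3.5, section 4.1.1.3 and footnote g, end the dated window for female participants at the later of two dates: last pembrolizumab dose + 120 days, and last regorafenib dose + 210 days. The standard-window gap then becomes 0 for every order of stopping. Leave the male-partner window as it is.

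Say plainly that this aligns the standard window only. For the 30-day cut-off after new anti-cancer therapy, the sponsor should either apply the same end date or state why the shorter one is kept. For a woman still in long-term follow-up, the undated duty in 10.4.3.2 may run past the new end date too, but the contraception period will then be over.

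The cost is wording in three places and in the safety reporting guide, plus a reporting duty up to 90 days longer for women under the standard window. No tests or visits are added, so capture after scheduled testing ends depends on the site learning of the pregnancy.

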8.3.6 Adverse Events of Special Interest

Selected non-serious and serious AEs are also known as Events of Clinical Interest (ECI) and must be reported to the sponsor.

ECI for this trial include:

- 1. Pembrolizumab overdose, as defined in Section 8.4, that is not associated with clinical symptoms or abnormal laboratory results
- 2. HECIs as defined in Section 6.6.2.1

8.4 Treatment of Overdose

Overdose of regorafenib

For this study, any dose of regorafenib greater than **160 mg** within one day will be considered an overdose.

In the event of an overdose, the investigator/treating physician should:

• Closely monitor the participant for any AE/SAE and laboratory abnormalities until study intervention can no longer be detected systemically.

Page 89 of 141

- Obtain a plasma sample for PK analysis within 3 days from the date of detection of overdose if requested by the sponsor (determined on a case-by-case basis).
- Any overdose or incorrect administration of study intervention should be noted on the Study Drug Administration eCRF.
- AEs associated with an overdose or incorrect administration of study intervention should be recorded on the AE eCRF.

Decisions regarding dose interruptions or modifications will be made by the investigator in consultation with the sponsor based on the clinical evaluation of the participant.

For detailed guidance on overdosing, refer to the most current version of the IB for regorafenib.

There is no specific treatment for regorafenib overdose. The highest dose of regorafenib studied clinically is 220 mg QD. The AEs observed at this dose were primarily dermatological events, hoarseness, diarrhea, mucositis, and nausea. In the event of suspected overdose, regorafenib should be immediately withheld and supportive care instituted under the supervision of a qualified health care professional.

Overdose of pembrolizumab

For this study, an overdose of pembrolizumab will be defined as any dose of 1000 mg or greater (\geq 2.5 times the study dose).

No specific information is available on the treatment of overdose of pembrolizumab. In the event of overdose, the participant should be observed closely for signs of toxicity. Appropriate supportive treatment should be provided if clinically indicated.

8.5 Pharmacokinetics

For all participants enrolled, sparse pharmacokinetic samples will be collected for determination of regorafenib and its metabolites M-2 and M-5 (in plasma) and pembrolizumab (in serum) as specified in Table 1–3.

Sampling times outside the suggested sampling time intervals will not be considered as protocol deviations. However, omission of samples specified in the PK sampling (Table 1–3) will be considered a protocol deviation. The date and clock time of each sample as well as dates and times of the regorafenib administration and start and stop times of pembrolizumab infusion will be recorded in the eCRF as PK estimates will be based on the sampling times relative to dosing times. If regorafenib is not administered on the day of PK sampling, the predose samples will be collected and the post-dose samples will not be collected.

Samples may be collected irrespective of any dose modifications during the treatment cycle. No detailed dosing history is required before the pre-dose sample, but the regorafenib dose that separates the pre- and post-dose sample needs to be taken under supervision and the time of dosing should be recorded. In addition, the time of meal intake prior to regorafenib administration on PK sampling days needs to be reported in the patient diary and together with the dosing time is recorded in the eCRF.

Regorafenib data from this study may be pooled with data from other clinical studies for pharmacometric analysis.

Model-determined exposures of regorafenib may be used for exposure-response analyses of selected measures of efficacy, safety or biomarker changes. The results of population PK and exposure-response analyses will be reported separately from the overall study results.

Page 90 of 141

The PK analyses will be performed using validated analytical methods. Exploratory measurements of other moieties may be performed, if needed.

PK samples for pembrolizumab will be held until the end of the study by the central lab. At that time, the determination will be made if analysis will be done on the samples, however, samples may be analyzed prior to the end of the study if safety or efficacy concerns arise.

Instructions for the collection, processing, storage and shipment of PK samples will be provided separately by the sponsor (e.g., sample handling sheets or laboratory manual).

